1. SYNOPSIS

Investigational Drug Product:	ALY688 Ophthalmic Solution
Active Ingredient:	ALY688
Study Title:	A Phase 1/2a, Randomized, Double-Masked, Vehicle-Controlled Study Evaluating the Safety and Exploratory Activity of Two Concentrations (0.1% and 0.4%) of ALY688 Ophthalmic Solution in Subjects with Dry Eye Disease
Study Number:	ALY688-201
Study Phase:	1/2a
Study Objectives:	
Primary objective: Evaluate the safety and tolerability of 2 concentrations of ALY688 in subjects with dry eye disease (DED) treated topically twice daily (BID) for 8 weeks.
 
Additional objective: Evaluate the efficacy of 2 concentrations of ALY688 in subjects with DED treated BID for 8 weeks.

Study Design:	
After meeting eligibility criteria during screening, qualified subjects will undergo a 14-day run-in period during which they will use Vehicle BID bilaterally. If they meet eligibility criteria at baseline, they will be randomized 1:1:1 to receive ALY688 0.1% (n=40), ALY688 0.4% (n=40), or Vehicle (n=40). Dosing will be BID bilaterally. If there are no clinically significant drug-related adverse tolerability changes on Day 3, subjects will continue dosing BID bilaterally for the remaining dosing period for a total of 8 weeks.
 
The study eye will be designated at randomization. If both eyes have an inferior corneal fluorescein staining score (ICSS) ≥ 2, the study eye will be the one with the greater ICSS. If both eyes have the same ICSS grade, the eye with the higher overall total corneal staining score will be selected. If both eyes show the same total corneal staining score, the eye with the lower tear volume by Schirmer's test will be selected; if both eyes still score equally, the right eye will be selected.
 
Ocular assessments should be conducted by the same assessor throughout a subject's participation period to reduce observer variability. All efficacy assessments will be carried out consistently either in the morning or the afternoon (preferred time window is ± 2 hours) throughout all study visits to minimize intra-subject diurnal variability.
 
During the Baseline visit, all assessments will be carried out before dosing with the study medication in order to serve as pre-study baseline. For on-treatment visits at Weeks 2, 4, and 8, all ocular assessments will take place at least 1 hour after receiving study medication. At Weeks 2, 4, and 8, subjects who arrive in clinic before 1 pm should receive their morning dose administered by clinic staff. Subjects who arrive in clinic after 1 pm should self-administer their morning dose and receive their afternoon/evening dose by clinic staff.
 
A subset of subjects (up to 36) at selected sites will undergo blood collection for pharmacokinetic evaluation of the test article at 3 timepoints (15 and 45 minutes and 3 hours) after final dose of study medication at Week 8.

Investigational Product, Dose and Mode of Administration:	
Topical, sterile, non-preserved single-use vials of 0.25 mL ocular eye drop:
 
 • ALY688 Ophthalmic Solution 0.1% • ALY688 Ophthalmic Solution 0.4% • Vehicle Ophthalmic Solution (same as ALY688 without active drug)

Study Population:	Subjects with symptomatic DED confirmed by clinical examination
Inclusion Criteria:	
 1. Males or females who are at least 18 years of age at the Screening visit 2. Subject-reported history of dry eye in both eyes for at least 3 months prior to screening 3. Confirmed use, by either medical records or subject self-reporting, of artificial tear substitute for symptoms of DED ≥ 3 times per week on average for the 4 weeks prior to screening (including regular or as needed use of prescription or over-the-counter products) 4. Willing to suspend use of artificial tear substitutes for the duration of study participation 5. Eye dryness score (EDS) using 0- to 100-point visual analog scale (VAS) in both eyes between 40 and 90 (inclusive) at screening and between 30 and 90 (inclusive) at baseline 6. One eye (same eye) must meet all of the following criteria at both screening and baseline: 
 a. Total corneal fluorescein staining score between 6 and 17 (inclusive) using the Expanded National Eye Institute (NEI) scoring system (0-20 scale) b. Inferior corneal fluorescein staining score (ICSS) ≥ 2 (0-4 scale) c. Schirmer's test (without anesthesia) score between 1 and 9 mm/5 min (inclusive) 7. Best-corrected visual acuity (BCVA) of $+0.6$ logarithm of the minimum angle of resolution (logMAR) or better (using Early Treatment Diabetic Retinopathy Study [ETDRS]); Snellen equivalent score of 20/80 or better) and reading Snellen visual acuity of 20/40 (J3) or better in each eye at screening and baseline 8. An understanding, ability, and willingness to fully comply with study procedures and restrictions 9. Ability to voluntarily provide written, signed, and dated (personally or via a legally authorized representative) informed consent to participate in the study 10. For females of childbearing potential, confirmation of a negative urine pregnancy test at screening and baseline and willing to comply with applicable contraceptive requirements detailed in the protocol
Exclusion Criteria:	Ocular history – medical

	
 1. Confluent (grade 4) fluorescein corneal staining in the superior zone in either eye at screening or baseline 2. Confluent (grade 4) fluorescein corneal staining in 3 or more zones in either eye at screening or baseline 3. Improvement in EDS by more than 25% between screening and baseline (run-in period) 4. Allergic conjunctivitis if active within 4 weeks prior to screening or anticipated to be active during the study 5. Severe meibomian gland dysfunction (MGD) using the Simplified Scheme for Grading MGD (based on central 10 gland orifices of each eyelid) with a score of Grade 3 or greater in the study eye evaluating both the upper and lower eyelids. The subject will be excluded if any of the following are present in either of the evaluated eyelids of the study eye: 
 a. Plugging of meibomian gland: more than 2/3 of glands plugged or >6 glands plugged in either eyelid of the study eye b. Character of secretion: paste or no observable expressate in either eyelid of the study eye c. Expressibility: fewer than 2 glands expressible in either eyelid of the study eye 
NOTE: Mild or moderate (Grade 1 or 2) posterior lid margin disease (MGD) is allowed if the subject has not received topical or systemic treatment (eg, tetracycline, doxycycline, or azithromycin) or mechanical therapy such as lid scrubs, for at least 4 weeks prior to screening and will not receive any such therapy during the study
 
 6. Glaucoma or ocular hypertension requiring treatment within 6 months of screening 7. Use of an intranasal tear stimulant (device or medication) within 4 weeks prior to screening or planned use during the study 8. Unwillingness to avoid wearing contact lenses starting at least 2 weeks prior to screening and during the study 9. DED secondary to scarring (eg, associated with irradiation, alkali burns, Stevens-Johnson syndrome, cicatricial pemphigoid) or destruction of conjunctival goblet cells (as with vitamin A deficiency) 10. Any other clinically significant ocular condition in the study eye that, in the investigator's judgment, is of a severity that adversely affects vision and/or could affect the results of study assessments, including but not limited to: eyelid margin abnormalities (eg, anterior blepharitis, excessive lid laxity, floppy eyelid syndrome, ectropion, entropion), retinal disease (eg, proliferative diabetic retinal disease [minimal early non-proliferative diabetic retinopathy is permitted], age-related macular degeneration [AMD; mild AMD untreated by intravitreal injection is permitted], or retinal vein occlusion), lagophthalmos, exposure keratitis, limbic keratoconjunctivitis, or active ocular or eyelid inflammation, including uveitis 11. Corneal stromal and/or epithelial defects or anatomic abnormalities that, in the investigator's judgment, adversely affect vision and/or could affect the results of study assessment not due to DED (eg, neurotrophic keratitis recurrent corneal erosions, and filaments) 12. Currently active, or history of, ocular herpes or any other ocular infection within 4 weeks prior to screening (with the exception of mild or moderate
--	--

	
MGD—see above) or if on medication to suppress herpes simplex virus (HSV)
 
13. Ocular trauma within 6 months prior to screening that, in the investigator's judgment, is of a severity that could affect results of study assessments
 
Ocular history – surgical
 
14. Have undergone laser in situ keratomileusis (LASIK) or other types of refractive surgery within 12 months prior to screening, or have persistent symptoms associated with LASIK surgery (neurotrophic etiology)
 
15. Have undergone penetrating keratoplasty, Descemet's stripping with endothelial keratoplasty, Descemet's membrane endothelial keratoplasty, or deep anterior lamellar keratoplasty in the study eye
 
16. Have a dissolvable punctal plug placed in the study eye within 3 months prior to screening
 
17. Have a non-dissolvable punctal plug placed in the study eye within 2 months prior to screening that is, in the investigator's judgment, considered to be unstable, irritating, likely to fall out (based on prior history of a lost plug), or cannot be replaced immediately if it falls out during the study
 
18. Have any planned ocular and/or lid surgeries during the study, including placement of new punctal plugs (replacement of non-dissolvable plugs that have fallen out is required)
 
19. Punctal cauterization within 12 weeks prior to screening
 
20. Prior ocular surgery or laser treatment within 6 months prior to screening NOTE: Glaucoma laser procedures are permitted up to 3 months prior to screening; yttrium aluminum garnet (YAG) capsulotomy is permitted up to 4 weeks prior to screening
 
21. Eyelid surgery within 12 months prior to screening
 
Prior medications
 
22. Any use within 4 weeks prior to screening of any ocular topical medications (excluding artificial tear substitutes)
 
23. Planned use of any ocular topical medications during the study (including artificial tear substitutes)
 
24. Any use within 4 weeks prior to screening or planned use during the study of any oral antibiotics (including tetracycline, doxycycline, or azithromycin) for the treatment of blepharitis or MGD
 
25. Use of the following therapies prior to or during the study:
 
 Topical brimonidine within 4 weeks prior to screening Topical cyclosporine within 6 weeks prior to screening Topical lifitegrast within 4 weeks prior to screening Any other topical ocular dry eye treatments 4 weeks prior to screening, with the exception of artificial tear substitutes The following treatments for MGD within 4 weeks prior to screening: thermal pulsation (Lipiflow), debridement of lid margin (BlephEx), or thermal application (MeiBoFlo, Tear Care) Any systemic (including oral) antibiotic 2 weeks prior to screening
--	---

	
 g. Initiation of oral omega fatty acid supplements within 3 months prior to screening or anticipated changes during the study h. Any use within 2 months prior to screening or planned use during the study of topical retinoids, such as retinol, tretinoin, adapalene, tazarotene, alitretinoin, and bexarotene i. Initiation within 4 weeks prior to screening of any medication (oral or topical) known to cause ocular drying or any anticipated change in dosing of such medication during the study j. Oral aspirin or aspirin-containing products or nonsteroidal anti-inflammatory drugs (NSAIDs) unless the subject is on a stable dose for 4 weeks prior to screening with no dose change anticipated during the study NOTE: Use of aspirin or NSAIDs on an as needed basis is allowed if it is no more than 3 doses per week; acetaminophen is allowed k. Systemic, inhalation, intranasal, or topical ocular corticosteroids within 4 weeks prior to screening and during the study. Dermatologic formulations are allowed l. Antihistamines (oral or ocular) within 4 weeks prior to screening or planned use during study participation m. Systemic immunosuppressive medications within 4 weeks prior to screening and during the study 
Product related
 
26. Known hypersensitivity to investigational product or its components
 
Systemically related
 
 27. Any known history of alcohol or drug abuse within 12 months prior to screening that, in the investigator's judgment, may interfere with the subject's participation in the study 28. Positive urine pregnancy test or nursing an infant (female subjects only) at screening or baseline 29. Any blood donation or significant loss of blood within 4 weeks prior to screening or planned donation during the study 30. History of immunodeficiency disorder, human immunodeficiency virus, hepatitis B or C, or evidence of acute active hepatitis A or organ or bone marrow transplant 31. History or presence of Sjogren's syndrome treated with systemic immunosuppressants NOTE: mild to moderate Sjogren's is permitted if untreated with medications within 3 months prior to screening and no planned treatment during the trial 32. Any other significant physical or mental illness or condition that, in the investigator's judgment, could interfere with study parameters, including but not limited to: poorly controlled diabetes or hypertension, active inflammatory or infectious condition, unstable cardiac disease, or active malignancy 33. Planned surgical procedure(s) during the study that, in the investigator's judgment, may interfere with the subject's participation in the study 34. Clinically significant abnormalities in laboratory tests at screening based upon the investigator's judgment
--	---

	
Administrative
 
35. Are employees, or immediate family members of employees, at the investigational site
 
36. Are members of the same household
 
37. Are unable or unwilling to follow instructions and participate in all study assessments and visits
 
38. Less than 80% compliance with BID bilateral Vehicle dosing during the 14-day run-in period (as determined by counting returned single-use vials at baseline)
 
39. Have used any investigational product or device within 4 weeks prior to screening or planned use during the study

Description of Study Sites:	Up to 150 subjects are planned to be enrolled across up to 12 sites throughout the United States.
Individual Subject Participation:	
Vehicle run-in period: 2 weeks
 
Treatment period: 8 weeks
 
Total: 10 weeks

Duration of Study:	Up to 4 months for recruiting plus 2 months for subject treatment, for a total of 6 months
Study Assessments:	
The following study assessments and procedures will be performed:
 
 • Informed consent • Medical/Ophthalmic history • Concomitant medications • Vital signs (blood pressure [BP] and heart rate [HR]) • EDS and ocular discomfort score (ODS) assessments by VAS • Symptom Assessment in Dry Eye (SAnDE) score assessment • Additional dry eye symptom assessment by VAS • BCVA assessment • Reading speed assessment • Slit lamp biomicroscopy • Conjunctival hyperemia grading • Tear film break-up time (TFBUT) • Corneal fluorescein staining • Conjunctival lissamine green staining • Schirmer's test (without anesthesia); strips to be retained for inflammatory marker analysis • Intraocular pressure (IOP) • Impression cytology • Multidimensional Psychological Questionnaire • Blood collection for laboratory testing, and pharmacokinetic evaluation in a subset of subjects • Urine pregnancy test (if applicable) • Urinalysis • Dilated fundus exam • Collect study drug and diary card

	
 • Compliance assessment • Inclusion/exclusion criteria assessment • Randomization • Study drug dispensing • Study drug administration (with post-instillation comfort VAS) • Adverse event assessment
Safety Endpoints:	
To evaluate the safety and tolerability of ALY688 administered BID over 8 weeks compared with Vehicle, as assessed by ocular examinations (including any changes from baseline in slit lamp biomicroscopy, dilated fundus exam, visual acuity, IOP, and post-dosing comfort) and systemic evaluations (AEs, BP and HR, clinical laboratory test results, and pharmacokinetic results [in a subset of subjects]) in subjects with DED.

Efficacy Endpoints:	
To evaluate the efficacy of ALY688 compared with Vehicle by the following measures:
 
 • Mean change from baseline at Weeks 2, 4, and 8 in total corneal fluorescein staining score using the NEI/Industry Workshop scale (0-20 scale). • Mean change from baseline at Weeks 2, 4, and 8 in EDS using a VAS (0-100 scale, both eyes) during the visit. 
NOTE: This will also be assessed by a daily EDS score card for the 7-day period prior to baseline and the Weeks 2, 4, and 8 visits. The mean of these scores for the 7 days prior to the Weeks 2, 4, and 8 visits will be compared with the mean of the scores for the 7 days prior to baseline.
 
Additional exploratory endpoints:
 
 • Mean change from baseline at Weeks 2, 4, and 8 in ICSS (0-4 scale) using the Expanded NEI/Industry Workshop scale (5 zones with 0-4 scale/zone) • Mean change from baseline at Weeks 2, 4, and 8 in ODS using a VAS (0-100 scale, both eyes) 
 ○ NOTE: This will be assessed in the same manner and at the same timepoints as the EDS score • Mean change from baseline at Weeks 2, 4, and 8 in SAnDE score (frequency and severity) based upon subject recollection for the week prior to visit • Mean change from baseline at Weeks 2, 4, and 8 in conjunctival lissamine green staining score using the NEI/Industry Workshop scale (6 zones with 0-4 scale/zone) • Mean change from baseline at Weeks 2, 4, and 8 in conjunctival hyperemia by clinical scoring (0-4 clinical grading scale using standardized grading photos) • Mean change from baseline at Weeks 2, 4, and 8 in TFBUT using fluorescein • Mean change from baseline at Week 2, 4 and 8 in tear volume as assessed by Schirmer's test (without anesthesia) • Mean change from baseline at Week 8 in the following components of the VAS dry eye symptom index: 1) burning/stinging, 2) itching, 3) foreign body sensation, 4) photophobia, and 5) pain. In addition,

	
the symptom that each subject self-identifies at baseline as the most bothersome will be analyzed separately.
 
 • Mean change from baseline at Week 8 in reading speed as assessed by New International Reading Speed Texts (IReST) in subjects with adequate near visual acuity (BCVA of 20/40 or better) and appropriate language comprehension • Mean change from baseline at Week 8 in conjunctival goblet and lymphocyte cell densities as assessed by impression cytology • Mean change from baseline at Week 8 in selected inflammatory markers in tears from retained Schirmer's tear strips (post hoc analysis) 
 ○ NOTE: Selected measures from those listed above will also be undertaken as part of the Screening visit to determine eligibility; refer to the Schedule of Events for specific evaluations
Analysis Populations:	
Safety and mITT populations: All randomized subjects who receive at least 1 dose of investigational product
 
Per protocol population: All randomized subjects who meet enrollment criteria and complete efficacy evaluations at week 4 or 8

Sample Size and Statistical Methods:	
This is an exploratory, hypothesis-generating study. However, with 40 subjects per group (N=120), there is 80% power to detect an effect size of 0.63 with a 2-sided, two-sample t-test at an alpha level of 0.05 (uncorrected for multiplicity).
 
A repeated measures analysis will be performed using the Wei-Lachin approach. In addition to repeated measures, the Week 8 change from baseline will be tested as a single timepoint measure. An aggregated efficacy measure (specific endpoints TBD) will be analyzed as a means to look for consistent trends and to increase the overall power. For example, an aggregate of ICSS, TFBUT, and Schirmer's test results may be analyzed.
 
The test of the several endpoints involves a comparison of mean change from baseline across visits. A fixed effects longitudinal model will be utilized where the data of both eyes will be used for measures evaluated in both eyes with measures repeated across visits. Baseline score will be a covariate in the model. An unstructured correlation matrix will be utilized for correlation between eyes and across visits. Measures that do not involve both eyes will utilize an unstructured matrix to model the correlation across visits.
 
The randomization will be stratified on study site to achieve a balance among treatment groups within a site. Each site will be preloaded with complete blocks. The site will dispense kits by Interactive Web Response System as subjects qualify for treatment assignment. To the extent possible, study drug resupply to sites will be done with complete block(s).
 
Statistical details will be specified more fully in the Statistical Analysis Plan.

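### Does the per-protocol set need treatment-period compliance and artificial-tear conditions?

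*Combined protocol and SAP*

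**What the plan says.** All the relevant text is in the synopsis.

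- **Analysis Populations.** Per protocol is "All randomized subjects who meet enrollment criteria and complete efficacy evaluations at week 4 or 8". Safety and mITT share one definition: "All randomized subjects who receive at least 1 dose of investigational product".
- **Study Design.** At Weeks 2, 4 and 8, "all ocular assessments will take place at least 1 hour after receiving study medication". To support this, "subjects who arrive in clinic before 1 pm should receive their morning dose administered by clinic staff"; later arrivals take the morning dose themselves and get the next one from clinic staff.
- **Exclusion Criteria.** Criterion 38 bars subjects with "Less than 80% compliance with BID bilateral Vehicle dosing during the 14-day run-in period", judged by returned vials at baseline. Criterion 37 bars those who "Are unable or unwilling to follow instructions and participate in all study assessments and visits". Criterion 23 concerns planned use of ocular topical products, artificial tears included. The opening of criterion 25 covers listed therapies both before and during the study.
- **Inclusion Criteria.** Criterion 4 reads "Willing to suspend use of artificial tear substitutes for the duration of study participation".
- **Study Assessments.** The list includes "Collect study drug and diary card", a compliance assessment and concomitant medications. None of them is tied to an analysis set.
- **Sample Size and Statistical Methods.** The study is described as exploratory, and fuller statistical detail is deferred to the SAP. No analysis is assigned to the per-protocol set.

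**The concern.** The name per protocol suggests subjects who were treated as planned. The stated rule checks eligibility and the presence of late efficacy data, but not what the subject did in between. The contrast with the run-in is striking: a subject just under 80% on Vehicle cannot be randomized, yet one who takes half the study drug can count as per protocol.

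Artificial tears raise the same question. Inclusion 3 requires regular tear use before screening, so every subject is a habitual user who is asked to stop. A return to tears could plausibly affect dryness scores and corneal staining, the two leading efficacy measures. Inclusion 4 and exclusion 23 test willingness and plans at entry, not conduct.

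The rule also omits the one-dose condition that mITT has, so as written the set is not formally contained in mITT.

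At stake is interpretation: a per-protocol result might be taken as the effect in adherent subjects when the set still contains clear deviators.

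**Working it through.** **1. The plan's own figure.** Inputs from Sample Size and Statistical Methods: 40 per group, effect size 0.63, two-sided alpha 0.05, two-sample t-test. Power is 79.5% by the noncentral t and 80.4% by the normal approximation, so the stated 80% reproduces. The plan gives 0.63 as the effect detectable with that power, not as an expected effect. It serves below only as a yardstick.

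**2. What the rule lets in.**
- Treatment period: 8 weeks × 7 days × 2 = 112 dosing occasions. Once-daily use gives 56/112 = 50%. Such a subject can be dosed in clinic, be assessed at Week 4, and qualify.
- Run-in: 14 × 2 = 28 occasions; 80% of 28 = 22.4. A subject with 22/28 = 78.6% fails exclusion 38.

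| Possible condition | Does the per-protocol rule supply it? |
|---|---|
| At least one dose | Not stated, but the Week 2, 4 and 8 visit procedure makes an undosed subject with Week 4 or 8 data unlikely |
| Treatment-period compliance | No; exclusion 38 covers the run-in only |
| No artificial tears on treatment | No; inclusion 4 and exclusion 23 concern intention at entry |
| No other prohibited medication on treatment | In part, since exclusion 25 extends to the study period for some items |
| Efficacy data at Week 4 or 8 | Yes |

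**3. Non-adherence left in the set.** Let q be the non-adherent share of an active arm and r the share of those who miss both Week 4 and Week 8. Both are assumptions. The remaining share is q(1 − r)/(1 − qr). Dilution is 0.63 × share if non-adherent subjects get no effect, and half of that if they get half the effect.

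| q | r | Remaining share | Dilution, no effect | Dilution, half effect |
|---|---|---|---|---|
| 10% | 75% | 0.025/0.925 = 2.7% | 0.017 SD | 0.009 SD |
| 15% | 50% | 0.075/0.925 = 8.1% | 0.051 SD | 0.026 SD |
| 20% | 25% | 0.150/0.950 = 15.8% | 0.099 SD | 0.050 SD |

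**4. Bias from excluding on compliance.** Suppose there is no true effect, 20% of active and 10% of vehicle subjects are excluded, and the tendency to be excluded has correlation ρ of 0.3 to 0.5 with poor outcome (all assumed). Excluding a share p raises an arm's mean by ρ × φ(z)/(1 − p), where z is the normal quantile at p.
- φ(z)/(1 − p) is 0.350 at p = 0.20 and 0.195 at p = 0.10; the difference is 0.155.
- False difference favouring active: 0.3 × 0.155 = 0.046 SD; 0.5 × 0.155 = 0.077 SD.
- If both arms lose the same share with the same ρ, this bias is zero.

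The bias range spans the mid-case no-effect dilution (0.051 SD) and lies above the mid-case half-effect dilution (0.026 SD). The largest dilution, 0.099 SD, exceeds it.

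**5. The denominator.** A threshold of 80% on all planned doses is 0.80 × 112 = 89.6. A fully compliant subject who leaves after Week 4 has had 4 × 7 × 2 = 56 occasions, or 50% of 112. On that denominator, a compliance rule would remove the Week-4-only subjects whom the stated rule deliberately admits.

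**The case for a change.** The strongest case for a change is that the gap is real and cheap to close. The entry criteria do not fill it for home dosing or for artificial tears, and the study already collects vials, diary cards, compliance and concomitant medications. A defined population invites use, and in a hypothesis-generating study a result under this label could influence later decisions.

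There is also a power argument. Take 0.63 as the effect in adherent subjects, no benefit in the others, and equal non-adherence in all arms. Keeping 5% non-adherent subjects among 40 per arm gives 75% power, against 77% with 38 per arm once they are removed. At 15% the figures are 66% and 73% (34 per arm).

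The reading of the text stands, and so does the caution about interpretation. The power gain of roughly 2 to 7 points does not settle the matter: it assumes that exclusion is unrelated to outcome, the very assumption a post-randomization compliance rule puts in doubt, and it concerns a set for which no test is stated. Nor is the change wording alone. The treatment-period compliance measure and its denominator would have to be chosen, and membership adjudicated before unmasking. The missing one-dose condition adds almost nothing, given dosing at the visits.

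**Conclusion.** The observation is accurate, but no change to the plan follows. As stated, the set contains eligible subjects with late efficacy data, which is a permissible definition. No stated result or conclusion depends on it: the supplied text gives it no analysis, safety is primary, efficacy is exploratory, and detail is left to the SAP, where analysts ordinarily settle deviation rules and set membership.

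A stricter definition is a trade-off rather than a clear improvement. The dilution that remains is about 0.02 to 0.10 SD if non-adherent subjects get no effect, and about 0.01 to 0.05 SD if they get half. The possible selection bias is about 0.05 to 0.08 SD in favour of active. These ranges overlap, and every rate and correlation behind them is assumed, so neither definition can be shown to be better. A comparison with dilution in mITT is not supportable either: no imputation is stated, and with observed data alone subjects without Week 8 measurements would not enter the single-timepoint Week 8 comparison.

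One caution on reading remains: unless the SAP adds adherence conditions, a result in this set should be described as one in eligible, evaluable subjects, not as the effect in those who took the treatment as planned.

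### Site is the randomisation stratum but not a named model term, and baseline adjustment is not stated for the Week 8 test or the endpoints listed only at Week 8 (a minor precision point)

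*Combined protocol and SAP*

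**What the plan says.** All of this is in the Synopsis (section 1).

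- **Longitudinal model.** Sample Size and Statistical Methods introduces it with "The test of the several endpoints involves a comparison of mean change from baseline across visits". It is a fixed effects model that uses both eyes where both are measured, with an unstructured correlation matrix. Its only named covariate is baseline: "Baseline score will be a covariate in the model".
- **Week 8 test.** The same section adds: "In addition to repeated measures, the Week 8 change from baseline will be tested as a single timepoint measure". It gives no method or covariate for this test.
- **Power statement.** The only two-group comparison named is the one used for sizing: "80% power to detect an effect size of 0.63 with a 2-sided, two-sample t-test", with 40 subjects per group.
- **Randomisation.** "The randomization will be stratified on study site to achieve a balance among treatment groups within a site", and "Each site will be preloaded with complete blocks". Description of Study Sites allows up to 12 sites. Site does not appear among the model terms.
- **Endpoints listed only at Week 8.** Efficacy Endpoints gives several, starting with "Mean change from baseline at Week 8 in the following components of the VAS dry eye symptom index" (five components). The others are the most bothersome symptom, reading speed, and goblet and lymphocyte cell densities. Tear inflammatory markers are also listed at Week 8 but are labelled post hoc, so they are left out of this point.
- **Deferral.** "Statistical details will be specified more fully in the Statistical Analysis Plan".

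**The concern.** Blocking by site makes the treatment groups more alike with respect to site. If outcomes differ between sites, the true variance of the treatment difference falls. An analysis without site still counts the between-site variation as noise, so its standard error is too large. The interval is then wider than it need be and the test rejects too rarely.

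Baseline adjustment raises a separate question. It is promised for a model described as working across visits, while the Week 8 test is introduced as something additional. An analyst could run that test as a model contrast, which carries the covariate, or as a raw comparison of change scores, which does not. The endpoints with one listed post-baseline visit leave the same choice open.

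What is at stake is precision at Week 8 with 40 subjects per arm, using baseline values and site identifiers that are collected anyway.

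**Working it through.** **Inputs from the documents:** 40 per group, standardised effect 0.63, two-sided alpha 0.05, 1:1:1 allocation, up to 12 sites.

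**Assumed, because the documents do not give them:** the correlation r between baseline and Week 8, the SDs, the site share of variance (ICC), and the block size. The 0.63 is not tied to an endpoint; it is taken here as the Week 8 change-score effect, with one value per subject.

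**1. The plan's own figure.** A normal approximation gives power 0.804. The noncentral t with 78 degrees of freedom and noncentrality 0.63 × √(40/2) gives 0.795. The stated 80% is reproduced.

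**2. Site omitted after stratification.** If site accounts for a share ICC of the variance and arms are balanced within site, the true standard error is √(1 − ICC) times the one reported. The actual type I error is 2[1 − Φ(1.96/√(1 − ICC))]. Power with site fitted uses a t-test with 78 − 11 = 67 degrees of freedom.

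| Assumed ICC | Type I error, site omitted | Power, site omitted | Power, site fitted |
|---|---|---|---|
| 0 | 0.050 | 0.804 | 0.793 |
| 0.05 | 0.044 | 0.811 | 0.813 |
| 0.10 | 0.039 | 0.817 | 0.833 |
| 0.20 | 0.028 | 0.831 | 0.874 |

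At ICC 0.1 the reported standard error is too large by a factor of 1/√0.9 = 1.054, or about 5%. The site-omitted power column is a normal approximation, so the ICC 0 row slightly overstates the cost of fitting site.

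Simulation (120 subjects, 12 sites, three arms, blocks of 3 with even sites or blocks of 6 with uneven sites) agrees. At ICC 0.1 type I error was 0.039–0.042 without site and 0.047–0.049 with it. At ICC 0 it was 0.049–0.051 either way.

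**3. Baseline adjustment of a Week 8 change.** The ratio of adjusted to unadjusted variance is V = SD8²(1 − r²)/(SDb² + SD8² − 2r·SDb·SD8), where SDb and SD8 are the SDs at baseline and Week 8 and r is their correlation in the enrolled subjects. The effective effect is 0.63/√V, with 77 degrees of freedom.

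Inclusion criteria restrict eye dryness score, corneal staining and Schirmer's at entry. For those, suppose the baseline SD is cut to 60% of an unrestricted SD of 1, with pre-restriction correlation ρ. Then V = (1 − ρ²)/[(1 − ρ²) + (1 − ρ)² × 0.36]:

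- ρ = 0.3: V = 0.91/1.0864 = 0.838, power 0.860
- ρ = 0.5: V = 0.75/0.84 = 0.893, power 0.838
- ρ = 0.7: V = 0.51/0.5424 = 0.940, power 0.818

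Against 0.795 the gain is 0.023 to 0.065. With equal SDs, V = (1 + r)/2, and r = 0.3, 0.5, 0.7 gives power 0.932, 0.895, 0.855; this is an upper bound. The Week 8-only endpoints have no entry limit on their own scales, so it is less remote for them, but still assumed. If the slope on baseline is 1, V = 1 and nothing is gained.

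**4. Both together (simulated, restricted range, two-arm comparison).**

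| ρ | ICC | Unadjusted | Baseline | Baseline + site |
|---|---|---|---|---|
| 0.3 | 0 | 0.791–0.800 | 0.852–0.860 | 0.844–0.846 |
| 0.5 | 0 | 0.792–0.795 | 0.831–0.834 | 0.816–0.826 |
| 0.7 | 0 | 0.796 | 0.812–0.813 | 0.797–0.805 |
| 0.3 | 0.1 | 0.799–0.808 | 0.862–0.871 | 0.870–0.883 |
| 0.5 | 0.1 | 0.804–0.807 | 0.843–0.846 | 0.856–0.866 |
| 0.7 | 0.1 | 0.801–0.806 | 0.821–0.823 | 0.835–0.843 |

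With slope 1 and no site effect, power went from 0.787–0.790 unadjusted to 0.767–0.777 with both terms, a loss of 0.013–0.020.

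**The case against.** The text reviewed is a synopsis that leaves statistical detail to the SAP. A reader might infer that these choices are never made; the text supports only that they are not stated here. That objection stands.

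A reader might also infer that the Week 8 test is an unadjusted t-test. The documents do not say so. The t-test appears only in the power statement, and sizing on a simple test does not commit the analysis to one. The baseline-adjusted model is described in the same section, and the Week 8 test can be read as a contrast from it. If so, the baseline part needs only a clarifying sentence and gains no power.

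Nor do the documents support saying that the longitudinal model cannot handle the Week 8-only endpoints. With one post-baseline visit it reduces to ANCOVA, and the section excludes no endpoint. The gap is that this is left unsaid.

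Finally, every gain rests on assumed values. Site terms cost a little if site does not matter and are about neutral at ICC 0.05 (−0.005 to +0.008). No document supports a particular ICC. This also stands and limits the claim to a modest one. It does not remove the basic point: when site is prognostic, a model without the stratum reports standard errors that are too large.

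**Conclusion.** The point holds as a minor precision improvement. The described model omits the factor on which randomisation is stratified. The consequence is conservative, with type I error about 0.04 at an assumed ICC of 0.1 and about 0.05 if site has no effect. It is not an inflated error rate, and an unadjusted comparison would be unbiased.

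Fitting site is roughly neutral for power at ICC 0.05 and adds about 0.01–0.03 at ICC 0.1. Baseline adjustment of the Week 8 test adds about 0.02–0.07 under the restricted-range assumptions, and nothing if the test is already a model contrast. These figures assume one value per subject, whereas the plan uses both eyes for bilateral measures.

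Efficacy is an additional objective in a study that calls itself exploratory, so this is a change the sponsor could make, not one on which the trial depends.

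**What to change.** State in the SAP:

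1. Site, as the randomisation stratum, is a term in the efficacy models. Very small sites are pooled by a rule set before unmasking.
2. For endpoints measured at Weeks 2, 4 and 8, the Week 8 test is the Week 8 contrast of the baseline-adjusted longitudinal model.
3. For endpoints listed only at Week 8, the analysis is the single-visit form of that model: ANCOVA on the endpoint's own baseline, keeping the between-eye correlation where both eyes are measured.

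This changes wording only and needs no new data. If site has no effect, the site terms cost about 0.003–0.016 of power. In the simulations, pooling sites with fewer than 6 subjects cut the uneven-site cost from about 0.016 to 0.008. If the slope on baseline is also 1, the total loss against an unadjusted test is up to about 0.02.
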